## 12. DATA SAFETY AND MONITORING

### 12.1 Data Management and Reporting

Participating institutions will be collaborating with Vanderbilt in patient accrual. Data will be collected using a centralized electronic case report form called ON-line Clinical Oncology Research Environment = Oncore [REDACTED]. Oncore is a highly secure, web based, cancer specific, and customizable system that provides fully integrative clinical data management and study administration capabilities developed in an ongoing collaborative effort with NCI designated Comprehensive Cancer Centers. It fully integrates study administration functionality including protocol tracking, patient registration, NCI reporting, review committee tracking, and SAE tracking, with clinical data management functionality including electronic case report forms (eCRF) design, clinical data capture, protocol and regulatory compliance monitoring. Also the system is capable in storing basic protocol information (e.g., IRB approval dates, dates for annual renewals, etc) and clinical trials research data. Oncore allows the investigator to define specific protocol requirements and generate data collection forms. Creation of the data collection form is done with a single button click after the parameters of an individual protocol have been specified. Oncore permits specification of study protocols, management of patient enrollment, clinical data entry and viewing, and the generation of patient or study-specific reports based on time stamping. OnCore is embedded with a comprehensive domain repository of standard reference codes and forms to promote standardization. The sources for the repository include CDUS, CTC, CDEs from NCI, ICD, MedDRA and various best practices from contributing NCI-designated Comprehensive Cancer Centers. OnCore provides several reporting features specifically addressing NCI Summary 3 and Summary 4 and other reporting requirements. Data may also be exported in a format suitable for import into other database, spreadsheets or analysis systems (such as SPSS). This system will be used to manage all VICCC clinical trials data. OnCore is maintained and supported in the VICC Clinical and Research Informatics Resource.

Specified members at each participating site will submit all pertinent regulatory documents to the Coordinating Center Data Manager, who will store it in a secure location.

The Principal Investigator or designee will inform Genentech as defined in the Safety and Data Exchange Agreement (SDEA) of any serious adverse event, and will inform the IRB in accordance with each institution's IRB policy. The investigator is responsible for the detection and documentation of events meeting the criteria and definition of an AE or SAE, as provided in this protocol. During the study when there is a safety evaluation, the treating investigator or site staff will be responsible for detecting, documenting, and report AEs and SAEs, as detailed in the protocol. If any problem is identified related to the conduct of this research, the VICC Data Safety and Monitoring Committee (DSMC) will be formally asked to review the study and the situation that required DSMC intervention.

## 12.2 Meetings

This trial will be monitored by the VICC Breast Cancer Research Team. The Breast Cancer Research Team is composed of the Clinical Core Director of the Breast Cancer Program and Team Leader, Surgical Oncologists, Radiation Oncologists, Medical Oncologists, Research Nurses, the Data Manager, and our Regulatory Specialist. The Breast Cancer Research Team meets on a monthly basis to discuss all AEs/SAEs, accrual, compliance, safety issues, adherence to protocol, reviews, etc. pertaining to all breast cancer studies. This particular study will be thoroughly reviewed during these meetings. These monthly meetings have minutes recorded each time and those are also reviewed on a monthly basis by the Breast Cancer Research Team Physician Leader.

Subsequent to the Breast Cancer Research Team Monthly Meeting, monthly teleconferences between participating site and the Breast Cancer research team at Vanderbilt will be held to discuss all issues related to the trial (AEs/SAEs, accrual, compliance, safety issues, adherence to protocol, reviews, etc.).

## 12.3 Monitoring

This trial will be monitored continuously by the study's Protocol Chair and by the Breast Cancer Research Team at VUMC. Quarterly safety and monitoring reports are available to the Data and Safety Monitoring Committee (DSMC) as determined by the VICC Scientific Review Committee (SRC). The DSMC reviews all adverse events reported during the previous month for all clinical trials active at the VICC and makes recommendations to address concerns of patient safety. The DSMC of the VICC SRC will submit an annual report to the VICC Director on activities of the preceding year and will make recommendations to improve data and safety monitoring activities as needed.

A Quality Assurance auditor under the direction of the DSMC will audit this clinical trial quarterly for compliance with adverse event reporting, regulatory and studies requirements, and data accuracy and completion. Audit reports detailing the findings are provided to the DSMC. Site visits to ensure compliance will be performed on an *ad hoc* basis, notably in high accruing centers.

## **12.4 Data Handling and Record Keeping**

### **12.4.1 Case Report Forms**

An electronic case report form (eCRF) is required and must be completed for each included participant. The completed dataset should not be made available in any form to third parties, except for authorized representatives of appropriate Health/Regulatory Authorities, without written permission from Vanderbilt.

### **12.4.2 Record Retention**

To enable evaluations and/or audits from Health Authorities and Vanderbilt, each site investigator agrees to keep records including: The identity of all participants (sufficient information to link records; e.g., hospital records), all original signed informed consent forms, copies of all source documents, and detailed records of drug disposition. To comply with international regulations, the records should be retained by the investigator in compliance with regulations.

During data entry, range and missing data checks will be performed on-line. The checks to be performed will be documented in the Data Monitoring Plan for the study. A summary report (QC Report) of these checks together with any queries resulting from manual review of the eCRF's will be generated for each site and transmitted to the site and the site monitor. Corrections will be made by the study site personnel. This will be done on an ongoing basis.

## **13. REGULATORY CONSIDERATIONS**

### **13.1 Informed Consent and Confidentiality**

The investigator (or his/her designee) will explain to each subject the nature of the study, its purpose, the procedures involved, the expected duration, the potential risks and benefits involved and any discomfort it may entail. Each subject will be informed that participation in the study is voluntary, that s/he may withdraw from the study at any time, and that withdrawal of consent will not affect her subsequent medical treatment or relationship with the treating physician(s) or institution. The informed consent will be given by means of a standard written statement, written in non-technical language, which will be IRB approved. The subject should read and consider the statement before signing and dating it, and will be given a copy of the document. No subject will enter the study or have study-specific procedures done before his/her informed consent has been obtained.

In accordance with the Health Information Portability and Accountability Act (HIPAA), the written informed consent document (or a separate document to be given in conjunction with the consent document) will include a subject authorization to release medical information to the Investigator Sponsor, Genentech and supporting agencies and/or allow these bodies, a regulatory authority, or Institutional Review Board access to subjects' medical information that includes all hospital records relevant to the study, including subjects' medical history.

The investigator agrees to keep all information provided by this study in strict confidence and to request similar confidentiality from his/her staff and the IRB/IEC/REB. Study documents

provided (protocols, investigators' brochures, CRFs and other material) will be stored appropriately to ensure their confidentiality.

Patient medical information obtained by this study is confidential, and disclosure to third parties other than those noted below is prohibited. Upon the patient's permission, medical information may be given to his or her personal physician or other appropriate medical personnel responsible for his or her welfare. This medical information must be made available to the IRB and DSMC, upon request, for source verification of study documentation. Data generated by this study must be available for inspection upon request by representatives of the U.S. FDA, local health authorities, [name] and her authorized representative(s), collaborators and licensees, and the IRB for each study site, if appropriate. We will make all reasonable efforts to keep patient's protected health information (PHI) private and confidential. We will only utilize or relinquish this kind of information according to federal privacy guidelines. There are many safeguards in place to prevent the unintentional disclosure of information obtained for or produced by this study. Research data, including the data collected from the medical charts will be entered into a password-protected database. Any publications or public disclosure of data relating to the patient's tumor will be done without any identifying information.

PHI will be collected and stored in the OnCore system. The coordinating center will have access to all research data, which will be kept for at least 2 years after the study is completed. Any research data entered in a patient medical record will be stored for an indefinite amount of time. There are no plans to destroy data at this time.

Confidentiality and security will be maintained for the tissue collection within this study. All tissue samples obtained for this study will be assigned a code and this code used to identify the sample. The samples will not be labeled with the patient's name, address or other information that would identify them. All information will be coded to maintain privacy. Research data, including the data collected from the medical charts will be entered into a password-protected database. The database (Breast Cancer Program Database) in which this study data is going to be stored has a firewall (in addition to the institutional firewall) with the highest level of protection, i.e. the same level of protection as the on-line hospital information system at Vanderbilt. This means that users must log on to a web server that sits between the institutional firewall and the firewall to the database, and only this application server is allowed to query the database. Information, including the identifier and password for the authorized users, is transmitted via a secure shell protocol using 128k encryption. Only [name], the PI, and the Breast Team Data Manager, approved through our institutional review board will be allowed access to patient identifiers. Other levels of authorization may exist for approved users, e.g. access to de-identified data. This database will store a de-identified link to the patient data and will not otherwise store patient data, even de-identified. The safety monitoring will be performed by the groups deemed appropriate by the Vanderbilt University Medical Center Institutional Review Board for reviewing the clinical trials procedure. Safety monitoring for the database is also performed by the Networking and Security Services of the Vanderbilt University Medical Center. Audit trails for access to the web server and the databases behind the dual firewall system are maintained in accordance with the practices of the Networking and Security Services of the Vanderbilt University Medical Center.

## 13.2 Ethics and GCP

This study will be carried out in compliance with the protocol and Good Clinical Practice, as described in:

1. ICH Harmonized Tripartite Guidelines for Good Clinical Practice 1996.
2. US 21 Code of Federal Regulations dealing with clinical studies (including parts 50 and 56 concerning informed consent and IRB regulations).
3. Declaration of Helsinki, concerning medical research in humans (Recommendations Guiding Physicians in Biomedical Research Involving Human Subjects, Helsinki 1964, amended Tokyo 1975, Venice 1983, Hong Kong 1989, Somerset West 1996).

The investigator agrees to adhere to the instructions and procedures described in it and thereby to adhere to the principles of Good Clinical Practice that it conforms to.

## 14. MULTI-CENTER GUIDELINES

### 14.1 Protocol Review and Amendments

Information regarding study conduct and progress will be reported to the Institutional Review Board (IRB) per the current institutional standards of each participating center.

Any changes to the protocol will be made in the form of an amendment and must be approved by the IRB of each institution prior to implementation.

The Protocol Chair (or her designee) is responsible for the coordination and development of all protocol amendments. Once approved by the Protocol Chair, Vanderbilt will disseminate this information to the participating centers.

### 14.2 Study Documentation

Each participating site is responsible for submitting copies of all relevant regulatory documentation to the Coordinating Center. The required documents include, but are not limited to the following: local IRB approvals (i.e., protocol, consent form, amendments, patient brochures and recruitment material, etc.), each participant's informed consent, enrollment form, eligibility checklist and tissue block registration, summary of unanticipated problems or protocol deviations, and documentation of expertise of the investigators. The Coordinating Center will provide each participating site with a comprehensive list of the necessary documents. It is the responsibility of the participating sites to maintain copies of all documentation submitted to the Coordinating Center.

The requirements for data management, submissions, and monitoring are outlined below. The participating sites will submit all the research related information (source documents and research records – IRB approval documents, patient registration list, CRF info, toxicity assessments, tumor measurements/ responses, etc.) to the Coordinating Center Data Manager, who will upload it on Oncore at the appropriate time points: prior to study initiation, when patients are enrolled, and monthly during study duration. Personnel from the VICC Clinical Trial Shared Resource will monitor the trial and may periodically visit the investigative site to assure

proper conduct of the trial and proper collection of the data. The investigators at other sites will allow the monitor to review all source documents used in the preparation of the case reports.

### **14.3 Records Retention**

U.S. FDA regulations (21 CFR §312.62[c]) require that records and documents pertaining to the conduct of this study and the distribution of investigational drug, including CRFs, consent forms, laboratory test results, and medication inventory records, must be retained by each Principal Investigator for 2 years after marketing application approval. If no application is filed, these records must be kept 2 years after the study is discontinued and the U.S. FDA and the applicable national and local health authorities are notified.

Following closure of the study, each participating center will maintain a copy of all site study records in a safe and secure location. The Coordinating Center will inform the investigator at each site at such time that the records may be destroyed.

### **14.4 Publication**

It is understood that any manuscript or releases resulting from the collaborative research will be circulated to the TBCRC Central Office and all participating sites and Genentech prior to submission for publication or presentation.

## **15. STATISTICAL CONSIDERATIONS**

### **15.1 Study Design/ Endpoints**

This is an open-label phase Ib/II multi-institution trial that evaluates the safety profile/ tolerability and efficacy of enzalutamide + taselisib in patients with metastatic triple negative (ER/PR/HER2 negative) breast cancer who are AR positive. As taselisib has not been evaluated with enzalutamide, we would begin with a phase Ib portion to ensure safety of the combination and to determine a recommended dose for phase II of taselisib when given in combination with enzalutamide at 160 mg/day. In the Phase II portion, we will randomize patients in a 3:1 ratio to enzalutamide + taselisib or enzalutamide only. AR positivity is defined as  $\geq 10\%$  of tumor cell nuclei with immunoreactivity for AR. Upon progression of disease by RECIST, patients on the combination arm will be discontinued from the study. Those on the enzalutamide alone arm can cross-over to receive enzalutamide + taselisib.

### **15.2 Phase Ib Study**

The taselisib dose will start at 2 mg/day (dose level 1) and enzalutamide at 160 mg/day. Dose escalation will proceed among cohorts of 3 patients according to a standard 3+3 algorithm beginning at the lowest dose level as described in Section 6.2.

In the phase Ib component of the trial, the MTD will be defined as the highest dose tested in which a DLT is experienced by 0 out of 3 or 1 out of 6 patients among the dose levels. The first cohort of patients (3 patients) in each arm will be started at dose level 1, and each patient will be observed for 4 weeks on the specified dose.

No new cohort of patients will be treated until the previous cohort has completed one cycle of therapy without any DLTs.

Once the phase Ib portion is completed, the safety data will be analyzed and the phase II component of the study will be completed to assess tolerability and efficacy of the study combination. Patients in the phase II component of the study will initiate study treatment at the MTD. Note that dose reduction within patients (individually) is allowed in the phase II component of the study (see dose modification section). Dose reduction will be required for a given patient in case of grade 3 or 4 toxicities. The phase Ib study will require approximately 15-24 patients.

### 15.3 Phase II Study

The primary endpoint of the phase II portion is to assess the CBR of enzalutamide + taselisib at 16 weeks. This will be studied using a Simon two-stage design. Because there is sparse data on single agent enzalutamide, we also plan to accrue patients to a single agent enzalutamide arm. Patients will be randomized to the dual therapy vs monotherapy arms using a 3:1 randomization. The coordinating center (VICC) will randomly assign patients to an arm. No direct comparison of the two arms will be conducted. Rather, the monotherapy arm will serve as an informal anchor when interpreting results, and will be especially informative when interpreting many of the secondary analyses.

We have designed the enzalutamide + taselisib arm as a Simon optimal two stage. This design allows for early termination for inefficacy. The antiandrogen bicalutamide, in a prior study with a similar patient population, resulted a CBR of approximately 20%. Thus, for this study, we aim to show an improvement in CBR from 20% to 40%. With a Type I error of 10% and a Type II error of 10%, we will accrue 17 patients in the first stage. After the first 17 patients in the phase II portion have completed 2 cycles and obtained scans, the data will be analyzed. If 4 out of the 17 have a response (CR, PR, or SD), we will expand the study to a total of 37. If, at the end of the trial, there are 11 out of 37 patients with response, we will deem the regimen worthy of further study. If there are 3 or few responses in the first 17 patients, the study will terminate early. If 10 or few responses are seen in the total of 37, the regimen will be deemed unworthy of further study. This study has a 55% probability of stopping early under the null hypothesis. Patients whose disease progresses within 30 days of starting the study without a DLT will be replaced during the phase I portion.

Concurrently, an arm of single agent enzalutimide will be accrued. For every 3 patients randomized to the enzalutamide + taselisib arm, 1 patient will be randomized to the enzalutamide only arm. If the dual therapy arm terminates early due to inefficacy, we will also terminate the monotherapy arm. Thus, this arm will have a minimum of 6 and a maximum of 12 patients. We do not plan to do any formal analysis on this group of patients.

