**PHASE I SCHEMA:**

**PHASE II SCHEMA:**

AR positive:  $\geq 10\%$  of tumor cell nuclei with immunoreactivity for AR in a CLIA certified laboratory

One cycle = 28 days, tumor assessment with scans will be performed after every 2 cycles

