- l Tumor assessment should be performed approximately every 2 cycles (up to -5 days) while on study treatment and at End-of-treatment visit if not obtained within the past 6 weeks. Scans should consist of CT scan of the chest, abdomen, and pelvis and a bone scan at baseline. Subsequent scans should consist of CT chest, abdomen and pelvis, and bone scan if bone metastases were present on the baseline studies. At the end of treatment, all scans (baseline and through disease progression) should be sent on a CD to the Vanderbilt Cancer Imaging Support Laboratory for central review and assessment. See Section 10.5 for details and address.
- m Archived tumor biopsy specimen: 20 unstained slides of archived biopsy block (unstained slides) or fresh tumor biopsy will be requested at the time of enrollment prior to initiation of treatment.
- n Tumor biopsies will only be performed in the phase II portion. A tumor biopsy from a metastatic site will be obtained from patients prior to day 1, at cycle 2 day 14-21, and upon progression of disease. The third biopsy (at the end of treatment) will not be required for patients who are removed from study for reasons other than disease progression. A patient who undergoes a research biopsy procedure for the purpose of this protocol, and in whom inadequate tissue is obtained, is not obligated to undergo a repeat biopsy.
- o See section 9.1. Required only for patients at Vanderbilt and only in the phase II portion. This should be performed prior to tumor biopsy, if possible. If MRI sub-study is not feasible due to scheduling, MRI weight limits, etc., patients may still continue with the remainder of the study.
- p Subjects on the enzalutamide + taselisib arm should begin enzalutamide on day 1 of cycle 1, and taselisib on day 1 of cycle 2.
- q Pill Diary can be found in the packet of supplemental forms.
- r See Section 6.4.2.
- s Phase II only. Biopsy questionnaire should be filled out by the patient on C3D1. Form can be found in the packet of supplemental forms.
- t The cycle 2 day 8 visit is only needed for patients on the combination of taselisib + enzalutamide. Patients on enzalutamide only do not need a visit on this day.

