#### *Phase II*

- To evaluate the efficacy, as measured by clinical benefit rate (CBR), of enzalutamide + taselisib in patients with AR+ TN MBC. CBR is defined as the proportion of patients with a best response of CR, PR, or stable disease (SD)  $\geq 16$  weeks.

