### 10.4 Duration of Response

- Duration of overall response: The duration of overall response is measured from the time measurement criteria are met for CR or PR (whichever is first recorded) until the first date that recurrent or progressive disease is objectively documented (taking as reference for progressive disease the smallest measurements recorded since the treatment started). The duration of overall CR is measured from the

time measurement criteria are first met for CR until the first date that recurrent disease is objectively documented.

- Duration of stable disease: Stable disease is measured from the start of the treatment until the criteria for progression are met, taking as reference the smallest measurements recorded since the treatment started.

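### The stage 1 futility look counts any stable disease at 8 weeks, but its 3/17 boundary and 55% stopping probability hold only for clinical benefit at 16 weeks

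*Combined protocol and SAP*

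**What the plan says.** Section 15.3 opens with the endpoint: "The primary endpoint of the phase II portion is to assess the CBR of enzalutamide + taselisib at 16 weeks". Section 2.1 gives the definition: "CBR is defined as the proportion of patients with a best response of CR, PR, or stable disease (SD"), with the stable disease required to last 16 weeks or more. Section 6.3 repeats the 16-week requirement. The 20% null rate, taken from an earlier bicalutamide study, and the 40% target are both stated in 15.3 as CBR rates.

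The stage 1 rule in the same section is different. On timing: "After the first 17 patients in the phase II portion have completed 2 cycles and obtained scans, the data will be analyzed". On what is counted: "If 4 out of the 17 have a response (CR, PR, or SD), we will expand the study to a total of 37". Three or fewer of 17 stops the trial, and 10 or fewer of 37 is a negative result. The stated property is: "This study has a 55% probability of stopping early under the null hypothesis".

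The time scale comes from the Phase II Schema: "One cycle = 28 days, tumor assessment with scans will be performed after every 2 cycles". Section 10.4 fixes how stable disease is timed: "Stable disease is measured from the start of the treatment until the criteria for progression are met".

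No section tells the analyst to wait for 16-week status at stage 1, or to replace an earlier SD with 16-week status where that is known.

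**The concern.** The look is triggered at 8 weeks for the last of the 17 patients, when stable disease of 16 weeks cannot yet have been observed. As written, stable disease at 8 weeks counts towards the four needed to continue. The boundary and the 55% were derived for one event and are applied to an easier one.

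This is the trial's only planned efficacy stop. Section 15.3 also closes the monotherapy arm early only if the combination arm stops, so a weak look prolongs both arms. Under Section 6.3.1 taselisib starts on day 1 of cycle 2, so for patients on that schedule the 2-cycle scan follows only about 4 weeks of the combination.

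A smaller gap affects the final count. Section 15.3 speaks only of responses at 37 patients. Section 15.7 lists stable disease without a duration and does not class SD shorter than 16 weeks as a failure.

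**Working it through.** **Inputs.** From 15.3: stop at ≤3 of 17; positive at ≥11 of 37; null CBR 20%, target 40%; type I and II error 10% each; stated early stopping 55%. From the Phase II Schema: 2 cycles = 2 × 28 = 56 days = 8 weeks. Assumed, because the documents do not give it: q, the probability of CR, PR or SD at 8 weeks when the true 16-week CBR is 20%.

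**1. The plan's own figure.** The probability of early termination (PET) is P(X ≤ 3 | n = 17, p = 0.20) = 0.0225 + 0.0957 + 0.1914 + 0.2393 = 0.549, which matches the stated 55%. Expected enrolment on the combination arm is 17 + 20 × (1 − 0.549) = 26.0. Exact type I error is 9.5% and power at 40% is 90.3%. A search over designs returns 3/17, 10/37 as the Simon optimal design for these inputs. The boundaries and the 55% therefore belong to an event with a 20% null rate.

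**2. Direction.** A patient whose benefit is SD of at least 16 weeks, or a response first seen after week 8, must be without progression at week 8. A patient with CR or PR at week 8 counts under both definitions. Missed scans aside, q ≥ 0.20, and q is strictly larger if any stable patient progresses between weeks 8 and 16. PET falls as q rises, so 55% is a ceiling.

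**3. Size if all 17 are judged on 8-week status or any SD.** PET = P(X ≤ 3 | 17, q); expected N = 17 + 20 × (1 − PET). The top value of q assumes a constant hazard: √0.20 = 0.447. Type I error is for a final count on the defined CBR, with CBR patients a subset of those without progression at 8 weeks.

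| q | PET | Expected N | Type I error |
|---|---|---|---|
| 0.20 (as designed) | 54.9% | 26.0 | 9.5% |
| 0.25 | 35.3% | 29.9 | 10.0% |
| 0.30 | 20.2% | 33.0 | 10.3% |
| 0.40 | 4.6% | 36.1 | 10.4% |
| 0.447 | 2.0% | 36.6 | 10.5% |

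The limit with no interim stop at all is P(X ≥ 11 | 37, 0.20) = 10.46%. The corresponding limit on power is P(X ≥ 11 | 37, 0.40) = 92.8%, so power does not fall.

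**4. Size if some patients are already mature.** Suppose k of the 17 have, and are judged on, 16-week status (event rate 0.20), and the other 17 − k are judged at rate q. PET is the probability that the two counts sum to 3 or fewer.

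| q | PET, k = 8 | Expected N, k = 8 | PET, k = 13 | Expected N, k = 13 |
|---|---|---|---|---|
| 0.25 | 44% | 28.2 | 50% | 27.0 |
| 0.30 | 34% | 30.2 | 45% | 28.0 |
| 0.40 | 18% | 33.4 | 36% | 29.8 |
| 0.447 | 13% | 34.5 | 32% | 30.6 |

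**5. Conditional case only.** If undated SD were also counted at the 11/37 rule, the chance of declaring a regimen with true CBR 20% worthy of further study would be 28%, 54%, 90% and 97% at the four assumed values of q.

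**The case against.** The strongest reply is that the final conclusion is protected. With the defined CBR at 37 patients, type I error is at most 10.46% against a nominal 10%, power is not reduced, and the maximum sample size is unchanged. What is lost is futility efficiency. All of that stands.

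Second, the size of the loss rests on an assumed q, and treating all 17 patients as immature is the extreme case. Earlier enrollees will have longer follow-up: Section 7.2.1.3 already reports on 8 phase II combination patients, and Section 15.4 lets phase Ib patients at the recommended dose count as evaluable. With 11 of 17 mature and q = 0.30, PET is 41% and expected N about 29. This narrows the loss but does not remove it: every mixed case falls short of 55%. It also supposes that 16-week status replaces earlier SD, which 15.3 does not say.

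Third, CR, PR or SD might be read as shorthand for CBR. The 2-cycle trigger rules that out, because the last patients enrolled could not be classified. For the final count the reply is stronger. The natural reading there is the defined CBR, which 15.7 names as the main analysis, so the figures in step 5 describe a reading the wording permits, not the likely one.

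Fourth, the 4-week exposure point is not uniform. Section 9.5 has the first ten combination patients at Vanderbilt starting taselisib on day 1, which does not agree with 6.3.1; those sections must be reconciled. The main argument does not depend on this.

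**Conclusion.** The concern holds. Section 15.3 states a 55% chance of stopping early under the null, and the rule written beside it does not deliver that. The direction follows from the definitions alone. The size depends on the unstated 8-week rate and on how many of the 17 patients have 16-week data. For assumed 8-week rates of 25% to 45%, PET is 35% to 2% if all are judged at 8 weeks, 44% to 13% if 8 are mature, and 50% to 32% if 13 are mature. The consequence is more patients treated with an inactive regimen, with expected enrolment up from 26 to between 27 and 37 across these cases. False-positive risk is essentially unchanged provided the final count is the defined CBR, which the text should say outright. This must be corrected, because it governs the trial's only planned efficacy stop.

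**What to change.** In Section 15.3, name one event at both stages: clinical benefit, meaning CR, PR or SD of at least 16 weeks. Run stage 1 when each of the first 17 combination-arm patients has had the scheduled 16-week (end of cycle 4) scan or has failed earlier. The 3/17 and 10/37 boundaries, the 55%, and the error rates then apply as stated.

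Say how the scan window is handled. The Study Calendar allows early scans: "Tumor assessment should be performed approximately every 2 cycles (up to -5 days) while on study treatment". Sixteen weeks is 112 days, so an on-schedule scan may fall on day 107. State that a patient stable at the scheduled 16-week scan, within that window, counts as a success. Section 10.4 runs SD until progression criteria are met, so this settles classification without changing the endpoint.

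In Section 15.7, state that SD lasting less than 16 weeks is a failure for CBR.

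Alternatively, keep the 8-week look, state and justify an 8-week null rate, derive the stage 1 boundary from it, and restate early-stopping probability, type I error and power. With 17 patients, the stopping boundary giving a PET nearest 55% would be ≤4 at q = 0.25 (57%), ≤5 at 0.30 (60%), ≤6 or ≤7 at 0.40 (45% or 64%), and ≤7 at 0.447 (48%), against the written ≤3.

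The cost is protocol and SAP wording. With the first option the interim decision comes about 8 weeks later. The documents plan no accrual hold, so that means either a short pause or a few more patients enrolled before the decision, which would offset part of the saving in expected enrolment.
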